### **Subject Completion/Withdrawal**

Subjects may withdraw from the study at any time. CHOP employees will be included as possible study participants because many of them are within the study inclusion criteria. To ensure that their study participation is completely voluntary, subjects will be assured that their participation is completely voluntary and taking part in this research is not a part of their CHOP work or duties. The Investigator may withdraw subjects who violate the study plan, or to protect the subject for reasons of safety or for administrative reasons. It will be documented whether or not each subject completes the clinical study. If the Investigator becomes aware of any serious, related adverse events after the subject completes or withdraws from the study, they will be recorded.

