### **Inclusion Criteria**

#### Participant/Guardian

- 1) Males or females age 18 to 75 years
- 2) Has harnessed/fastened a child into a car seat in the last 5 years
- 3) Valid drivers license

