### **Exclusion Criteria**

#### Participant

- 1) Participant is not fluent in written and/or spoken English
- 2) Participant cannot install a safety seat due to a physical limitation

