## **Potential Benefits of Participation**

Participants may benefit indirectly through the findings from this study that may help to improve correct use of child safety seats.

At the end of the study visit, participants will be provided with resource sheet with some tips and links to resources about how to correctly harness a child into a child safety seat, such as the CHOP site: <https://www.chop.edu/centers-programs/car-seat-safety-kids>. Participants will not receive custom feedback about their harness installation, since not all members of the study team are certified Child Passenger Safety Technicians.

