## **Recruitment Strategy**

Participants will be recruited using a variety of methods. Our primary recruitment mechanism will be the CHOP Recruitment Enhancement Core (REC). The REC will e-blast possible participants with necessary recruitment information. We may also use the Pediatric Research Consortium (PeRC) for additional recruitment if needed to attain the sample size needed. Additionally, flyers and tear-pads may be posted in areas frequented by individuals in target groups (e.g., local shopping areas where allowed, on CHOP campus) as well as on websites and social media. The ad which has been prepared for websites will be posted on a number of websites frequented by local residents of our target population, including (but not limited to): CHOP network website and other CHOP affiliated sites and Facebook. Lastly, an email blast will be sent to a large portion of faculty and staff as well as other members of the CHOP care network.

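### Staff are eligible and emailed, but neither exclusion removes certified car-seat technicians, project staff or prior prototype users; the likely cost is modest sensitivity and generalisability, cheaply avoided

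*Protocol*

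**What the plan says.** - **Staff may take part.** Subject Completion/Withdrawal: "CHOP employees will be included as possible study participants because many of them are within the study inclusion criteria". The safeguard that follows concerns voluntariness only.
- **Staff are approached.** Recruitment Strategy: "an email blast will be sent to a large portion of faculty and staff as well as other members of the CHOP care network". This is the last channel listed; the primary one is the site's Recruitment Enhancement Core.
- **There are two exclusions.** "Participant is not fluent in written and/or spoken English" and "Participant cannot install a safety seat due to a physical limitation".
- **Experience is a floor with no ceiling.** Beyond age and a driving licence, the Inclusion Criteria require: "Has harnessed/fastened a child into a car seat in the last 5 years". Parenthood is not required, so a technician could qualify through work alone.
- **Some of the study team are technicians.** Potential Benefits of Participation withholds individual feedback "since not all members of the study team are certified Child Passenger Safety Technicians", which implies that some members are certified. The same section refers participants to the site's car-seat web page.
- **Screening is narrow.** Sections 3.1.1 and Screening & confirmation of eligibility confine the phone screen to what is needed to apply the eligibility criteria.
- **Experience is recorded after consent.** The Intake Survey (5.1.4) includes earlier installation and harnessing experience. It lists no item on certification or on earlier contact with the prototype.

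**The concern.** The trial compares people who work through three misuse scenarios with the app against people who do so without it, and errors left at the end of a scenario are among the assessments. The Study Device section aims the system at caregivers who commit critical misuses. Someone trained to detect those misuses may correct them unaided and so has little left to gain from the app. Each such person takes one of about 90 evaluable places and says little about the target user.

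People who already know the prototype raise a different problem: whatever they show, it is not what a first-time user would show.

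Staff cannot easily handle this informally. Because the phone screen is tied to the listed criteria, without an exclusion there is no clear basis for asking about certification or for declining a technician. Removing such a person after randomisation would be hard to defend.

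**Working it through.** **The plan's own figure.** The protocol expects about 100 enrolled to give at least 90 evaluable. Those two numbers imply a 10% loss: 90 / (1 − 0.10) = 100. This confirms the arithmetic only. The text at hand gives no effect size, alpha, power or control rate, so the 90 itself cannot be re-derived.

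**Can such people enter?** Take a staff technician aged 18 to 75, with a licence, who has harnessed a child within five years. Every inclusion criterion is met and neither exclusion applies. The same holds for a project colleague or a prior user of the prototype. The answer is yes.

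**Size of the dilution.** Only the 90 comes from the protocol. The rest is assumed: equal allocation (45 per arm), one binary outcome per participant, two-sided alpha 0.05, ordinary caregivers succeeding in 50% (control) and 80% (app), and a share f of experts who always succeed in both arms.

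- Control rate: q0 = 0.5(1 − f) + f
- App rate: q1 = 0.8(1 − f) + f
- Difference: q1 − q0 = 0.3(1 − f)
- Power = Φ[(q1 − q0 − 1.96·SE0) / SE1], where SE0 = √(2·q̄(1 − q̄)/45), SE1 = √([q0(1 − q0) + q1(1 − q1)]/45) and q̄ = (q0 + q1)/2

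For f = 0: SE0 = √(2 × 0.65 × 0.35 / 45) = 0.1006 and SE1 = √((0.25 + 0.16)/45) = 0.0955. Then (0.30 − 0.197)/0.0955 = 1.08, and power is 86.0%.

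| Experts | q0 | q1 | Difference (points) | Power |
|---|---|---|---|---|
| none | 0.500 | 0.800 | 30.0 | 86.0% |
| 1 of 90 | 0.506 | 0.802 | 29.7 | 85.3% |
| 2 of 90 | 0.511 | 0.804 | 29.3 | 84.7% |
| 3 of 90 | 0.517 | 0.807 | 29.0 | 84.0% |
| 5% | 0.525 | 0.810 | 28.5 | 83.0% |

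**Sensitivity to the assumed rates.** At a 5% share, 40% v 70% takes power from 82.8% to 79.0%, and 30% v 60% from 82.8% to 78.2%. Over the three pairs of rates the loss at 5% is therefore about 3 to 5 points.

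**Sensitivity to perfect expertise.** If experts succeed in 80% without the app and 95% with it (again assumed), three of 90 give q0 = 0.510, q1 = 0.805 and power 85.1%.

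**Prior users of the prototype.** If familiarity helps only those given the app, control stays at 50% and the app rate becomes 0.8(1 − f) + f. At f = 5% that is 81%, so the contrast grows from 30 to 31 points. If what they learned also lets them succeed without the app, they behave like the experts above and the contrast falls to 28.5. The sign is open.

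**The case against.** The case against has weight.

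- **Thin evidence of experts in the pool.** The statement that "not all members of the study team are certified Child Passenger Safety Technicians" describes the study team, not the staff who receive the email. Nothing suggests that team members would enrol, and no section describes earlier testing of the prototype by outsiders. This stands, and it is why no share can be claimed.
- **Not every outcome has a ceiling.** Load-cell tightness and time in seconds are also recorded. The text at hand does not show which outcome is primary, and the statistical section that the protocol cites is not in it. This stands: the binary calculation is an illustration.
- **Partly handled.** Earlier experience is collected and a baseline install precedes the scenarios, so description or adjustment is possible. This stands in part. The listed survey topics do not clearly identify technicians or prior users, and adjustment does not give back a place already used.
- **Broad eligibility is legitimate.** It is, and nothing in the protocol contradicts itself here. The proposal leaves employees in general eligible.

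A reader might infer that experts will succeed in both arms and will shrink the app effect substantially. The same model gives 79.8% power at a 10% share and 72.5% at 20%. But 20% of 90 is 18 people, and nothing in the protocol points to such numbers or says how experts would perform. A reader might also infer bias between the arms. Randomisation rules that out on average.

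**Conclusion.** The gap is real: staff are eligible and approached, and no criterion removes certified technicians, project staff or prior users of the prototype. The consequence is a possible, modest loss of sensitivity from technicians, and a loss of generalisability from both technicians and prior users. It is not confounding, and for prior users even the direction of the effect on the contrast is unknown.

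Under the 50% v 80% model, one to three experts cost about 1 to 2 points of power and a 5% share about 3 points. These figures rest on assumed rates, equal arms, a single binary outcome and perfect expert success, and the 5% share is itself illustrative. The point is a cheap improvement to eligibility. It does not put the trial's validity in doubt.

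**What to change.** Add one line to the Exclusion Criteria: current or past certification as a Child Passenger Safety Technician, work on this project, or earlier use of the prototype seat or app. Ask it as one item in the existing phone screen, which the new criterion then justifies. State that other employees remain eligible.

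The cost is one line, one question and a few volunteers turned away. A weaker fallback is to record certification and earlier exposure at screening or intake. That allows these participants to be described or examined separately, but they would still take up evaluable places.

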### **Early Termination Study Visit**

If a participant withdraws at any point during the Study Visit, they will receive full compensation for their time and effort. If a participant withdraws prior to the study visit, they will not receive compensation.

## **STUDY EVALUATIONS AND MEASUREMENTS**

### **Screening and Monitoring Evaluations and Measurements**

#### **Initial Contact**

Potential participants who learn about our study through our recruitment efforts may reach out to the study team if they are interested in participating. They may email or call the study team and leave their contact information. Information may include: First and Last Name, Phone Number(s), and Email Address(es). Potential participants are not required to provide this information during their initial contact with the study team; however, if provided, this information will be collected by the study team to aid in further communication efforts.

#### **Verbal Consent**

Participants who confirm eligibility and interest in participating will then be asked to verbally consent to study procedures. A member of the research team will explain the study to the participant and answer any questions they may have. Documentation of verbal consent will be recorded and retained for all participants. Once the participant is enrolled, they will be invited to complete an intake survey, and scheduled for their study visit.

### 5.1.4 Intake Survey

All participants will complete an intake survey that will collect data on a variety of car seat measures - current use, behaviors, knowledge, and preferences; and basic sociodemographics. Measures will include:

- Age (years)
- Sex
- Race/Ethnicity
- Self-reported crash history of self
- Household income
- Previous experience installing safety seats and harnessing children into them
- Risk perceptions about child occupant safety
- Barriers and facilitators to safety seat use
- Knowledge and attitudes about existing child occupant safety programs and policies

### Efficacy Evaluations

#### 5.2.3 Harness Installations & Assessments

Each participant will complete three (3) misuse scenarios using child safety seats during the study visit.

The assessment of each misuse scenario (n=3) will capture the following information:

Method of harness (e.g., direction of pull to tighten, if the participant checks the tightness or makes adjustments, if participant asks child about tightness)

Length of time (in seconds) to harness

Tightness of harness in control seat (measured by a load cell and pinch test)

Tightness of harness in intervention seat (measured by the number of lights achieved in tensioning, a load cell and pinch test)

Difficulties observed (e.g., participant is unable to get child to cooperate, participant is unable to tighten harness because of physical limitations, or angle of seat makes it difficult to harness child)

Errors present at end of scenario

A series of questions for the participant on their experience during the scenario

#### 1.1.2 Post-observation interview

We will collect the following information from each participant in an interview format after completing all three scenarios. Surveys may be collected via paper or direct data entry into REDCap. Interviews may be recorded on video.

- Facilitators or barriers they experienced while installing and harnessing the doll into the seat
- Ease of installation and harnessing
- What they liked or did not like about the app
- Belief of correct installation and harnessing technique
- Perceived errors in each scenario

## **STUDY DEVICE**

### **Description**

The proposed innovative child safety seat user engagement system designed to actively educate, instruct and alarm caregivers with information associated with automatically-sensed safety seat misuses/errors is highly innovative and address an important unmet need. The goal is to prevent child safety seat critical misuses and reduce deaths and injuries in children riding in motor vehicles. Critical misuses are a major public health concern and include: improper child weight for seat type, improper seat orientation, insecure attachment of the seat to the vehicle, and insecure harnessing of the child. Parental education, how, when, or where parents learned to install seats, and improved graphics/labeling on seats/manuals have been observed to have no significant effect on many critical misuses. Better systems are needed to improve the rate of proper seat use. A key enabling technology that makes the proposed sensor system possible at this time is newly-available extremely low-cost cellular radio modules that can achieve secure internet connectivity directly from the seat. This cellular radio will be built into an inexpensive pre-configured sensor system capable of sensing key state-of-use information, including the most common critical misuses, to automatically push usage and environmental information to a cloud-based server. The use of cellular technology eliminates the need for users to pair the seat with a cell phone or wi-fi network to achieve connectivity: the sensor system will operate right out of the box.

## **SAFETY MANAGEMENT**

### **Clinical Adverse Events**

Clinical adverse events (AEs) will be monitored throughout the study.

### **Adverse Event Reporting**

Since the study procedures are not greater than minimal risk, SAEs are not expected. If any unanticipated problems related to the research involving risks to subjects or others happen during the course of this study (including SAEs) they will be reported to the IRB in accordance with CHOP IRB SOP 408: Unanticipated Problems Involving Risks to Subjects. AEs that are not serious but that are notable and could involve risks to subjects will be summarized in narrative or other format and submitted to the IRB at the time of continuing review.

## **STUDY ADMINISTRATION**

### **Treatment Assignment Methods**

#### **Randomization**

Participants will be randomly assigned to either the intervention group or control group upon their arrival to the study visit. The randomization sequence was generated using SAS software, version 9.4 (SAS Institute, Cary, NC, USA).

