#### 3.1.2 Study Treatment Phase

Eligible participants will be asked to verbally consent to study procedures over the phone. Verbal consent will be documented in REDCap. Once the participant is enrolled, they will be allocated to either the control or intervention group. A research assistant will send the participant an invitation to complete the Intake Survey via REDCap prior to the study visit. If participants have not completed this intake survey prior to their study visit, they will be asked to complete the survey in-person before moving on to the intervention phase.

There will be a one-time study visit, which will take place in a study room on the 4th floor of the Roberts Center for Pediatric Research. The intervention phase of the visit will take place in a study room on the 4th floor.

A member of the study team will meet the participant in the Roberts Center for Pediatric Research parking lot or lobby. The study team member will escort the family to the 4th floor study room. Next, the team member will explain the click tight car seat system and demonstrate it to the participant. The participant will then be asked to do a full install of the car seat prior to completing the misuse scenarios. The participant will then be asked to complete three misuse scenarios. Participants in the intervention group will use the app while participants in the control group will complete the scenarios without the app.

Misuse scenarios will be evaluated by a member of the study team, including measuring harness tightness with a load cell and the pinch test (this will be a yes/no formatted question indicating whether the harness passed the slack test) and asking the participant to see the app once they are finished the scenario. In addition, after each misuse scenario is complete, participants will be asked to complete a brief survey about their experience. Participants will also complete a brief interview at the end of their study visit to understand more about their preferences.

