### Allocation to Treatment Groups and Blinding

This study will use a control and intervention group. Each enrolled participant will experience each of the three misuse scenario's once.

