### **Study Visit**

Study visits will take place at the CHOP Roberts Center for Pediatric Research and will not exceed 90 minutes. The following events will take place at the study visits:

Click tight technology explanation by study staff

Initial car seat install- baseline

First misuse scenario

Study team assessment

Reaction Survey

Second misuse scenario

Study team assessment

Reaction Survey

Third misuse scenario

Study team assessment

Reaction Survey

Preference and Experience interview

Participant debrief

Provide participants with remuneration for time and effort

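### Assignment is made on arrival, before the common demonstration and baseline install, and nothing conceals the arm until the scenarios begin

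*Protocol*

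**What the plan says.** The Randomization section of the protocol (under Study Administration) fixes the moment of assignment: "Participants will be randomly assigned to either the intervention group or control group upon their arrival to the study visit". Section 3.1.2 (Study Treatment Phase) gives an earlier moment, in its account of phone consent and enrolment: "Once the participant is enrolled, they will be allocated to either the control or intervention group".

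Section 3.1.2 then describes the visit. A team member meets the participant and escorts them to the study room. "Next, the team member will explain the click tight car seat system and demonstrate it to the participant". After that: "The participant will then be asked to do a full install of the car seat prior to completing the misuse scenarios". The arms separate only in the scenarios: "Participants in the intervention group will use the app while participants in the control group will complete the scenarios without the app".

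The Study Visit section lists the same order. Its first event is "Click tight technology explanation by study staff" and its second is "Initial car seat install- baseline"; the three misuse scenarios follow.

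The section headed Allocation to Treatment Groups and Blinding says "This study will use a control and intervention group" and that each participant meets each scenario once. It states no blinding or concealment of the arm from anyone.

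**The concern.** The demonstration and the initial install are common to both arms and, on the stated design, need no assignment. Assigning beforehand exposes them to knowledge of the arm without any gain. A demonstrator who knows that the app is coming might explain less, or explain more to a control participant to compensate. A participant who expects the app might attend less closely. Someone who learns that they are in the control group might be readier to leave.

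Any such difference arises before the outcomes are recorded and is carried into the comparison. With only two arms, it cannot be told apart from the effect of the app. Adjusting for the baseline install would not be a safe repair, because that install itself follows both the assignment and the demonstration.

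The same timing affects losses. Physical inability to install a seat is an exclusion criterion, but eligibility is screened by phone, so the initial install is the first practical test of it. The Early Termination Study Visit section also provides for withdrawal during the visit. As written, anyone lost at these steps has already been randomised.

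**Working it through.** No formula applies and the plan gives no figure to reproduce. The check is of the order of events.

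| Step | Timing in Randomization section | Timing in section 3.1.2 |
|---|---|---|
| Phone consent and enrolment | before assignment | assignment made here |
| Intake survey, if done before the visit | before assignment | after |
| Arrival | assignment made here | after |
| Intake survey, if done at the visit | after | after |
| Staff explanation and demonstration | after | after |
| Initial install (baseline) | after | after |
| Misuse scenarios 1 to 3 (app or no app) | after | after |

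1. The two sections conflict on when allocation happens and must be reconciled. Choosing either one does not settle the present point, because the demonstration and baseline install follow assignment in both columns.
2. The first step for which section 3.1.2 states an arm difference is the first misuse scenario. Assignment is therefore made at least two steps earlier than that statement requires.
3. Neither the Randomization section nor the Allocation and Blinding section keeps the assignment closed between arrival and the first scenario, and no other section does. None describes a scripted demonstration. The section on potential benefits notes that not every team member is a certified child passenger safety technician, so uniform delivery cannot be presumed from certification.
4. One passage complicates the picture. Section 5.2.3 distinguishes a control seat from an intervention seat, the latter with tensioning lights. The protocol does not say which seat is demonstrated or used for the initial install. If each arm has its own seat from the start, the run-in is itself arm-specific and assignment cannot simply be deferred.

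**The case against.** The strongest reply is that the document shows an opportunity for bias, not bias. Four stronger readings might be inferred, and the text does not support them.

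- **That the demonstrator knows the arm.** No section says so. Section 3.1.2 describes one demonstration for everyone, with no arm-specific content. The text supports only that nothing prevents the knowledge.
- **That a baseline taken after randomisation is biased in itself.** It is not, if both arms have been treated alike up to then and neither staff nor participant acts on the assignment. The initial install is not among the efficacy assessments in section 5.2.3, which concern the three scenarios, and no section makes it an outcome or covariate. Any such use could be set out in a statistical analysis plan that is not shown.
- **That the demonstration teaches exactly the skill tested.** It covers the seat system and leads to a seat install, whereas section 5.2.3 is mainly about harnessing. Errors at the end of a scenario may include installation errors, so overlap is possible but not established.
- **That the gap between about 100 enrolled and at least 90 evaluable measures the losses at issue.** Those counts start at phone enrolment and can include people who never attend. Nothing places a loss between arrival and the first scenario.

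It is also fair to say that later assignment would not blind the scenarios. Staff assess them and ask to see the app, so the arm is evident when outcomes are recorded.

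These points limit the claim but do not remove it. The run-in is the part of the visit where concealment is still achievable, and the protocol does not secure it. The timing of assignment is a protocol procedure, not a detail left to the analysis plan.

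**Conclusion.** The point holds as a design weakness that should be corrected. Assignment precedes two common steps that, on the difference stated in section 3.1.2, do not need it, and the arm is not concealed during them. Coaching, effort or withdrawal may therefore differ by arm in a way that analysis cannot separate from the app effect.

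The harm is potential. Its size and direction cannot be derived from the document, which gives no rate of errors, of withdrawal or of failed initial installs by arm. The conclusion assumes that the same seat can serve both arms during the run-in. If section 5.2.3 means that the seats differ from the start, the concern remains but the remedy changes.

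**What to change.** 1. In the Randomization section, replace the arrival timing with: after the seat demonstration and the baseline install, immediately before the first misuse scenario. State that the assignment is opened only then. Participants who withdraw or prove unable to install during the run-in are then not randomised.
2. Align the allocation sentence in section 3.1.2, which also removes its conflict with the Randomization section.
3. State that both arms use the same seat for the demonstration and the baseline install, and reconcile this with the control and intervention seats named in section 5.2.3.
4. If the seats must differ by arm from the start, use a scripted, identical demonstration in both arms instead of deferring assignment.

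The cost is small. The change is a few sentences of protocol text; the SAS-generated sequence is used in the same order, and the planned numbers do not change. The practical downside is that assignment and app set-up happen in mid-visit. Item 3 costs more only if the visit is now run with a different seat in each arm from the beginning.
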